### **A. Objective**

Roche Cobas Liat Flu/RSV POC Assay and procalcitonin testing as part of a stewardship intervention optimizes antiviral treatment and reduces antibiotic treatment for ED patients (under 50 years of age) with suspected influenza or RSV v. standard care using a prospective, patient-randomized design. In addition to the primary outcome, we will evaluate secondary outcomes including aggregate physician adherence to CDC guidelines for the treatment of influenza, antibiotic duration, hospital admission, and emergency department (ED) return visits within 30 days for patients diagnosed with influenza and RSV. Additional secondary outcomes would include time to resolution of symptoms, return to school/work, and subsequent healthcare utilization (e.g. doctor visits) obtained through patient self-report.

Hypothesis: The rapid waived POC assay and procalcitonin, as part of a stewardship intervention will lead to reduced antibiotic treatment by 20 percentage points compared to the control group for antibiotic non-responsive conditions including ILI and nonspecific URI and will increase appropriate antiviral treatment of patients with influenza at high risk recommended to receive treatment by 20 percentage points.

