#### **E. Study Endpoints**

[figure not shown]
The primary study endpoint is the determination of whether use of the Roche Liat Flu/RSV Assay and procalcitonin testing, as part of a stewardship intervention optimizes antiviral treatment and reduces antibiotic treatment for ED patients with suspected influenza. The secondary study endpoints are aggregate physician adherence to CDC guidelines for the treatment of influenza, antibiotic duration, hospital admission, ED return visits within 30 days for patients diagnosed with influenza and RSV, time to resolution of symptoms, return to school/work, and subsequent healthcare utilization (e.g. doctor visits) obtained through patient self-report.

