## LRTI Initial Antibiotic Use Algorithm

The second arm will be standard care.

Physicians and patients will not be blinded to test type. Tests will be performed on a real-time basis in the ED. All results will be delivered via standard of care through the EMR.

For each of these groups, data of the frequency and duration of antibiotic administration, antiviral use, adherence to evidence based guidelines for treatment of influenza, disposition, concomitant diagnoses, isolation, hospitalizations, and unscheduled return visits or readmissions within a 30 day period will be collected and compared. In addition, we will compare procalcitonin levels for patients diagnosed with RSV or influenza by the Roche LIAT in the test arm compared to those found to have evidence of bacterial infection based on chest xray, blood culture, and other ancillary tests. Where not recommended, reason for antibiotic use will be documented by the pharmacist and abstracted from chart review.

Research coordinators will contact patients and/or parents at 1 and 4 weeks after enrollment for self-reported secondary outcomes including symptom resolution, return to school/work, and follow up healthcare visits, medication adherence (to antibiotics and/or antivirals), and adverse events.

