#### **P. Statistical Analysis**

We will use standard descriptive statistics to summarize patient characteristics at randomization; mean and standard deviation (SD) for continuous variables and frequency and proportion for categorical variables. We will indicate the count of missing data for each variable. For the comparison of the primary outcomes, we will use frequency and proportions by arm, and compute a point estimate for the difference along with 95% confidence interval (CI) and p-value. We will stratify analysis based on flu status. For primary analyses (unstratified), we will use a Chi-square test (and Fisher exact test), and for stratified analyses, we used Mantel-Haenszel method. Secondary outcomes will be performed similarly. Statisticians and other investigators will remain blinded to treatment identity (e.g., data analyses with A/B coding). For all analyses, we will use SAS 9.4 (SAS Institute, Cary, NC).

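### Section P gives only proportion methods and extends them to all secondary outcomes, which does not suit time to symptom resolution or antibiotic duration

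*Combined protocol and SAP*

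**What the plan says.** Section P sets out proportions by arm, a difference with 95% CI and a p-value. For the tests it says "For primary analyses (unstratified), we will use a Chi-square test (and Fisher exact test"), with Mantel-Haenszel for the analysis stratified by flu status. The secondary outcomes get one sentence: "Secondary outcomes will be performed similarly". Mean and SD appear in Section P only for patient characteristics at randomization. On missing values it says "We will indicate the count of missing data for each variable" and nothing more.

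The outcomes this must cover include some that are not proportions. Section E lists "antibiotic duration, hospital admission, ED return visits within 30 days" and also "time to resolution of symptoms, return to school/work". Section A has the same symptom outcome: "Additional secondary outcomes would include time to resolution of symptoms, return to school/work".

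On collection, Section F (under the LRTI Initial Antibiotic Use Algorithm heading) will gather "data of the frequency and duration of antibiotic administration". It adds: "Research coordinators will contact patients and/or parents at 1 and 4 weeks after enrollment for self-reported secondary outcomes including symptom resolution".

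**The concern.** Admission, ED return and adherence are yes/no outcomes, and the stated methods serve them well. Time to symptom resolution is a time observed through two calls, and antibiotic duration is a number of days. Neither can be put through a chi-square test without first being reduced to a proportion, and the plan names no such reduction and no alternative.

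Two things are at stake. For symptoms, a test at one call discards what the other call shows, and which call is more informative depends on how fast symptoms resolve, which is not known in advance. For duration, the quantity being compared is not identified. Days per randomised patient and course length among treated patients are different quantities and can move in opposite directions. Return to school or work raises the same question as symptoms if it is defined as a time.

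**Working it through.** **1. The plan's own figure.** Section C gives 100 per arm for 80% power to detect 20 percentage points. With two-sided 5% (not stated; taken from the 95% CI) and the least favourable pair, 60% v 40%: n = [1.96·√(2·0.5·0.5) + 0.842·√(0.24 + 0.24)]² / 0.20² = 97 per arm, and power at 100 is 81.2%. The figure reproduces. It concerns the binary primary outcomes and is not in dispute.

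**2. Symptoms: inputs.** From the documents: 100 per arm, calls at weeks 1 and 4. Assumed, because the documents give nothing: exponential times to resolution, control median m of 5, 7 or 10 days, and hazard ratio (HR) for resolution of 1.2 or 1.5. The proportion resolved by day t is 1 − 2^(−t/m) in control and 1 − 2^(−t·HR/m) with intervention.

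Example, m = 7, HR 1.5: 50.0% v 64.6% at day 7, and 93.8% v 98.4% at day 28. Closed-form power at day 7: pooled SE √(2·0.573·0.427/100) = 0.070 and unpooled SE √((0.250 + 0.229)/100) = 0.069, so Φ[(0.146 − 1.96·0.070)/0.069] ≈ 55%. Simulation gives 57%.

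The grouped log-rank test combines two 2×2 tables by Mantel-Haenszel: resolved or not by week 1, then, among those still unresolved, resolved or not by week 4. Simulated power (20,000 trials):

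| HR | Median (d) | Grouped log-rank | Day 7 only | Day 28 only | Gain over better call |
|---|---|---|---|---|---|
| 1.5 | 5 | 66.4% | 61.7% | 11.4% | 4.7 |
| 1.5 | 7 | 68.2% | 56.7% | 38.0% | 11.5 |
| 1.5 | 10 | 69.3% | 49.0% | 58.3% | 11.0 |
| 1.2 | 5 | 19.2% | 16.9% | 6.1% | 2.3 |
| 1.2 | 7 | 19.7% | 16.5% | 12.4% | 3.2 |
| 1.2 | 10 | 20.2% | 13.5% | 17.4% | 2.8 |

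The better call switches from day 7 to day 28 as the median lengthens. With no effect (median 7) the grouped test rejects in 4.8%.

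**3. Unreached patients: hypothetical.** Suppose no true effect, median 7, and 25% v 15% unreached at week 4. Counting them as unresolved gives 0.9375·0.75 v 0.9375·0.85, a false difference of 9.4 points, and rejects in 33%. Available-case analysis and the grouped test reject in about 5%. That holds only while loss is unrelated to outcome. If one arm misses 22% of resolved and 70% of unresolved patients, the available-case proportion there is 0.731/(0.731 + 0.019) = 97.5% against 93.75%. Available-case analysis then rejects in 19% and the grouped test in 6%.

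**4. Duration: days per randomised patient, untreated = 0.** Assumed: fraction treated p, mean course μ days, SD 2 days among treated. The mean is pμ, the variance is p(4 + μ²) − (pμ)², the SE is √((v₁ + v₂)/100), and power is Φ(d/SE − 1.96).

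| Scenario | Means | Variances | SE | Power |
|---|---|---|---|---|
| Length only, 8 v 6 d, 50% treated | 4.0 v 3.0 | 18, 11 | 0.539 | 46% |
| Length only, 8 v 7 d, 50% treated | 4.0 v 3.5 | 18, 14.25 | 0.568 | 14% |
| Starts only, 50% v 30%, 8 d | 4.0 v 2.4 | 18, 14.64 | 0.571 | 80% |
| Both, 50% v 40%, 8 v 6 d | 4.0 v 2.4 | 18, 10.24 | 0.531 | 85% |

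Simulation with a bootstrap CI gives 47%, 13%, 79% and 85%.

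**5. Duration: dichotomising, hypothetical.** Power at cuts of ≥1, ≥5, ≥7 and ≥10 days is 6/28/83/80% for length only (8 v 6 d) and 83/81/67/20% for starts only, so the best cut depends on the unknown effect. Taking the best of the four afterwards rejects in 13% with no effect, against about 5% for one pre-set measure.

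**6. Why treated-only length is descriptive.** Per 100 patients, let 5-day courses fall from 25 to 5 while 10-day courses stay at 25. No course is shortened, yet the treated-only mean rises from 375/50 = 7.5 to 275/30 = 9.2 days, while days per patient fall from 3.75 to 2.75.

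**The case against.** The strongest reply is that *similarly* means the same reporting format (estimate, 95% CI, p-value) suited to each type of variable, so that duration would naturally get a mean difference. That reading is open. It removes the suggestion of an error but leaves the measure unnamed, and step 6 shows that the choice of measure can reverse the direction.

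A reader might infer that duration will be dichotomised at a convenient cut, or that unreached patients will be counted as unresolved. The documents propose neither. The 13% and 33% false-positive rates therefore describe what could happen under rules no one has written down, and the 33% also needs an invented imbalance in loss. A missing cut-point or a missing rule for unreached patients is, taken alone, missing detail.

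It is also fair that proportions at weeks 1 and 4 match the call schedule, so the symptom gain is an improvement in efficiency and not the repair of an invalid test. Days per randomised patient is debatable too. It partly restates antibiotic use, already a primary target, and a cut at ≥7 days would beat it when only length falls (83% v about 46%) or when both fall (about 95% v 85%). These points stand, and they limit what can be claimed for duration.

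**Conclusion.** The point holds as a mismatch between method and outcome: Section P names only proportion methods and extends them to two outcomes that are a time and a quantity. For symptoms there is a concrete, better method using data already planned. Its gain is about 5 to 12 power points at HR 1.5 and 2 to 3 at HR 1.2, assuming exponential times, medians of 5 to 10 days and 100 per arm. For duration the supportable conclusion is narrower: treat it as a quantity and fix one measure in advance. No measure is best under every effect.

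The stronger reading, that the plan as written inflates false positives, is not supported, because it needs rules the documents do not contain. Only secondary outcomes of a trial described as a pilot are affected. The primary tests, the sample size and the binary secondary outcomes stand as planned. This is worth changing before unblinding, but it does not threaten the trial.

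**What to change.** Keep the proportion methods for the binary secondary outcomes and add a few sentences to Section P.

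- **Time to symptom resolution** (and return to school or work, if defined as a time): a grouped or interval-censored log-rank test with hazard ratio from the week-1 and week-4 calls, or Kaplan-Meier and log-rank if resolution dates are recorded. Censor unreached patients at last contact. Treat a patient missed at week 1 but resolved at week 4 as interval-censored. State the non-informative-loss assumption. Any sensitivity analysis that counts unreached patients as unresolved should carry the warning that unequal loss alone can create a difference.
- **Antibiotic duration:** analyse as a quantity, with one measure fixed before unblinding and a statement of whether days are prescribed, administered or taken. One option is antibiotic-days per randomised patient (untreated = 0), as a mean difference with 95% CI, acknowledging that it blends starts with length. Report course length among treated patients descriptively only.

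The cost is a little text and analysis time and, if not already asked, one question on the resolution date at each call. The statistical price is reliance on non-informative loss for symptoms, and low power of days per patient if only course length changes.
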